## **10.3** Responsibilities of the investigator and IRB/IEC

Before initiating a trial, the investigator/institution must obtain approval/favorable opinion from the IRB/IEC for the trial protocol, documented informed consent form, consent form updates, subject recruitment procedures (eg, advertisements) and any other written information to be provided to patients/subjects. Prior to study start, the investigator is required to sign a protocol signature page confirming his/her agreement to conduct the study in accordance with these documents and all of the instructions and procedures found in this protocol and to give access to all relevant data and records to Novartis monitors, auditors, Novartis Quality Assurance representatives, designated agents of Novartis, IRBs/IECs, and regulatory authorities as required. If an inspection of the clinical site is requested by a regulatory authority, the investigator must inform Novartis immediately that this request has been made.

## **10.4 Publication of study protocol and results**

The key design elements of this protocol will be posted in a publicly accessible database such as clinicaltrials.gov. In addition, upon study completion and finalization of the study report the results of this trial will be either submitted for publication and/or posted in a publicly accessible database of clinical trial results.

## 10.5 Quality Control and Quality Assurance

Novartis maintains a robust Quality Management (QM) system that includes all activities involved in quality assurance and quality control, including the assignment of roles and responsibilities, the reporting of results, and the documentation of actions and escalation of issues identified during the review of quality metrics, incidents, audits and inspections.

Audits of investigator sites, vendors, and Novartis systems are performed by Novartis Pharma Auditing and Compliance Quality Assurance, a group independent from those involved in conducting, monitoring or performing quality control of the clinical trial. The clinical audit process uses a knowledge/risk based approach.

Audits are conducted to assess GCP compliance with global and local regulatory requirements, protocols and internal SOPs, and are performed according to written Novartis processes.

## 11 **Protocol adherence**

This protocol defines the study objectives, the study procedures and the data to be collected on study participants. Additional assessments required to ensure safety of patients/subjects should be administered as deemed necessary on a case by case basis. Under no circumstances including incidental collection is an investigator allowed to collect additional data or conduct any additional procedures for any purpose involving any investigational drugs under the protocol, other than the purpose of the study. If despite this interdiction, data, information, observation would be incidentally collected, the investigator shall immediately disclose it to Novartis and not use it for any purpose other than the study, except for the appropriate monitoring on study participants.

Investigators ascertain they will apply due diligence to avoid protocol deviations. If an investigator feels a protocol deviation would improve the conduct of the study this must be considered a protocol amendment, and unless such an amendment is agreed upon by Novartis and approved by the IRB/IEC and health authorities, where required, it cannot be implemented.

### 11.1 **Protocol Amendments**

Any change or addition to the protocol can only be made in a written protocol amendment that must be approved by Novartis, health authorities where required, and the IRB/IEC prior to implementation. Only amendments that are intended to eliminate an apparent immediate hazard to patients/subjects may be implemented immediately provided the health authorities are subsequently notified by protocol amendment and the reviewing IRB/IEC is notified. Notwithstanding the need for approval of formal protocol amendments, the investigator is expected to take any immediate action required for the safety of any patient included in this study, even if this action represents a deviation from the protocol. In such cases, the reporting requirements identified in Section 7 Safety Monitoring must be followed.

# 13 Appendix 1: Clinically notable laboratory values and vital signs

Only selected lab parameters which have potential to be sensitive to AMG 334 exposure are listed.

•	•		
Laboratory Variable	Gender (M/F/Both)	Standard Units	SI Units
LIVER FUNCTION AND RELATED VARIABLES			
SGOT (AST)	F	>93 U/L	>93 U/L
SGOT (AST)	Μ	>111 U/L	>111 U/L
SGPT (ALT)	F	>90 U/L	>90 U/L
SGPT (ALT)	Μ	>123 U/L	>123 U/L
Total bilirubin	Both	>3.6 mg/dL	>63 mmol/L
Alkaline Phosphatase	F	>832 U/L	>832 U/L
Alkaline Phosphatase	Μ	>1032 U/L	>1032 U/L
HEMATOLOGY VARIABLES			
Neutrophils	Both	<1.5x 10³/uL	<1.5x10  /L

Table 13-1	Clinically notable laboratory values
------------	--------------------------------------

# 14 Appendix 2: Liver event and Laboratory trigger Definitions and Follow-up Requirements

Table 14-1         Liver Event and Laboratory Trigger Definitions			
Definition/ threshold			
LIVER LABORATO TRIGGERS	
 
ORY
 
3 x ULN < ALT / AST ≤ 5 x ULN
 
1.5 x ULN < TBL ≤ 2 x ULN
 
		
LIVER EVENTS	• ALT or AST $> 5 \times$ ULN		
	• ALP > $2 \times ULN$ (in the absence of known bone pathology)		
	• TBL > 2 × ULN (in the absence of known Gilbert syndrome)		
	• ALT or AST > $3 \times$ ULN and INR > 1.5		
	• Potential Hy's Law cases (defined as ALT or AST > 3 × ULN and TBL > 2 × ULN [mainly conjugated fraction] without notable increase in ALP to > 2 × ULN)		
	• Any clinical event of jaundice (or equivalent term)		

- ALT or AST > 3 × ULN accompanied by (general) malaise, fatigue, abdominal pain, nausea, or vomiting, or rash with eosinophilia
- Any adverse event potentially indicative of a liver toxicity\*

\*These events cover the following: hepatic failure, fibrosis and cirrhosis, and other liver damagerelated conditions; the non-infectious hepatitis; the benign, malignant and unspecified liver neoplasms TBL: total bilirubin; ULN: upper limit of normal

Table 14-2Follow Up Requirements for Liver Events and Laboratory Triggers			
Criteria	Actions required	Follow-up monitoring	
Potential Hy's Law case a	
 
Discontinue the study treatment immediately
 
Hospitalize, if clinically appropriate
 
Establish causality
 
Complete liver CRF
 
	ALT, AST, TBL, Alb, PT/INR, ALP and γGT until resolution c (frequency at investigator discretion)	
> 8 × ULN	
 
Discontinue the study treatment immediately
 
Hospitalize if clinically appropriate
 
Establish causality
 
Complete liver CRF
 
	ALT, AST, TBL, Alb, PT/INR, ALP and γGT until resolution c (frequency at investigator discretion)	
> 3 × ULN and INR > 1.5	
 
Discontinue the study treatment immediately
 
Hospitalize, if clinically appropriate
 
Establish causality
 
Complete liver CRF
 
	ALT, AST, TBL, Alb, PT/INR, ALP and γGT until resolution c (frequency at investigator discretion)	
> 5 to ≤ 8 × ULN	
 
Repeat LFT within 48 hours
 
If elevation persists, continue follow-up monitoring
 
If elevation persists for more than 2 weeks, discontinue the
 
	ALT, AST, TBL, Alb, PT/INR, ALP and γGT until resolution c (frequency at investigator discretion)	

	

study drug

Establish causality

Complete liver CRF

	
> 3 × ULN accompanied by symptoms b	
 
Discontinue the study treatment immediately
 
Hospitalize if clinically appropriate
 
Establish causality
 
Complete liver CRF
 
	ALT, AST, TBL, Alb, PT/INR, ALP and γGT until resolution c (frequency at investigator discretion)
> 3 to ≤ 5 × ULN (patient is asymptomatic)	
 
Repeat LFT within the next week
 
If elevation is confirmed, initiate close observation of the patient
 
	Investigator discretion Monitor LFT within 1 to 4 weeks
ALP (ISOlated)		
> 2 × ULN (in the absence of known bone pathology) TBL (isolated)	
 
Repeat LFT within 48 hours
 
If elevation persists, establish causality
 
Complete liver CRF
 
	Investigator discretion Monitor LFT within 1 to 4 weeks or at next visit
> 2 × ULN (in the absence of known Gilbert syndrome)	
 
Repeat LFT within 48 hours
 
If elevation persists, discontinue the study drug immediately
 
Hospitalize if clinically appropriate
 
Establish causality
 
Complete liver CRF
 
	ALT, AST, TBL, Alb, PT/INR, ALP and γGT until resolution c (frequency at investigator discretion) Test for hemolysis (eg, reticulocytes, haptoglobin, unconjugated [indirect] bilirubin)
> 1.5 to ≤ 2 × ULN (patient is asymptomatic)	
 
Repeat LFT within the next week
 
If elevation is confirmed, initiate close observation of the patient
 
	Investigator discretion Monitor LFT within 1 to 4 weeks or at next visit
Jaundice	
 
Discontinue the study treatment immediately
 
	ALT, AST, TBL, Alb, PT/INR, ALP and γGT until resolution c (frequency at investigator discretion)

Novartis	Confidential	Page 64
Clinical Trial Protocol (Version 00)		Protocol No. CAMG334A2302
	

Hospitalize the patient

Establish causality

Complete liver CRF

	
Any AE potentially indicative of a liver toxicity*	
 
Consider study treatment interruption or discontinuation
 
Hospitalization if clinically appropriate
 
Establish causality
 
Complete liver CRF
 
	Investigator discretion
a Elevated ALT/AST > 3 × 1 b (General) malaise, fatigue c Resolution is defined as a values at three subsequen maximum of 6 months, (4)	ULN and TBL > 2 × ULN but without not e, abdominal pain, nausea, or vomiting, an outcome of one of the following: (1) r at monitoring visits at least 2 weeks apa b liver transplantation, and (5) death.	table increase in ALP to > 2 × ULN or rash with eosinophilia eturn to baseline values, (2) stable rt, (3) remain at elevated level after a

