#### Table 6-1Assessment Schedule

Period	Scree	ning	Treatment			Follow-Up		
Visit Name	Screening	Baseline	Treatment	Week 2 	Week 4	Week 8	End of Treatment	Follow-Up
Visit Numbers 	1	20	110	120	130	140	150 and TD/PSD	1999
Days	-42 to -28	-28 to -1	Day 1	14	28	56	84	168
Weeks	-6 to -4	-4 to -1	1	2	4	8	12	24
Informed consent	Х							
Medical history/current medical conditions	Х	Х						
Demography	Х	Х						
Safety Follow up Call				Х				
Physical Examination	Х	Х	Х		Х			Х
Vital signs and body measurements 	Х	Х	Х		Х	Х	Х	Х
Electrocardiogram (ECG)	Х		Х		Х		Х	
Hematology	Х		Х		Х		Х	Х
Clinical Chemistry	Х		Х		Х		Х	Х
Pregnancy Test (serum)	Х						Х	
Pregnancy test (urine)		Х	Х		Х	Х		Х
Urinalysis	Х							
Urine Drug Screen	Х							
Hepatitis screen ₄	Х							
Anti-AMG 334 antibodies			Х		Х		Х	Х
Columbia-Suicide Severity Rating Scale (C-SSRS)	Х	Х	Х		Х	Х	Х	Х
Beck Depression Inventory-II (BDI-II)	Х							
Randomization			Х					
Study drug administration			Х		Х	Х		
Clinical Outcome Assessment(s)					X 			

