#### 6.5.1.1 Hematology

The following parameters will be measured at the frequency outlined in Table 6-1: red blood cells (RBCs), nucleated RBCs, hemoglobin, hematocrit, MCV, MCH, MCHC, RDW, reticulocytes, platelets, white blood cells (WBCs), WBC differential. The differential will measure: bands/stabs, neutrophils, eosinophils, basophils, lymphocytes, monocytes, myeloblasts, promyelocytes, myelocytes, metamyelocytes, and atypical lymphocytes.

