#### 6.5.1.2 Chemistry

The following parameters will be measured at the frequency outlined in Table 6-1: sodium, potassium, chloride, bicarbonate, total protein, albumin, calcium, magnesium, phosphorus, glucose, BUN/urea, bilirubin (direct and total), alkaline phosphatase, ALT (SGPT), AST (SGOT), total cholesterol, HDL, LDL, triglycerides, CPK, and eGFR.

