#### 6.5.1.3 Urinalysis

The following parameters will be measured at the frequency outlined in Table 6-1: specific gravity, pH, blood, protein, glucose, bilirubin, WBC, RBC, epithelial cells, bacteria, casts, and crystals.

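### Table 14-2 requires an immediate stop for ALT/AST > 3 × ULN with INR > 1.5, but the protocol calls for INR only in liver-event follow-up, so an asymptomatic patient at > 3 to ≤ 5 × ULN could be managed as a laboratory trigger and dosed again

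*Protocol*

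**What the plan says.** Protocol Appendix 2 sorts raised ALT/AST into two classes. In Table 14-1, a value above 3 and up to 5 × ULN is a laboratory trigger. The same table makes ALT or AST "> $3 \times$ ULN and INR > 1.5" a liver event.

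Table 14-2 attaches very different actions to the two:

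- For the INR row, the first action is "Discontinue the study treatment immediately".
- For the asymptomatic > 3 to ≤ 5 × ULN row, the first action is "Repeat LFT within the next week". If the rise is confirmed, the patient is observed closely. Further monitoring is of LFTs, at the investigator's discretion.

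The scheduled laboratory tests are listed in Section 6.5.1:

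- The chemistry list ends "alkaline phosphatase, ALT (SGPT), AST (SGOT), total cholesterol, HDL, LDL, triglycerides, CPK, and eGFR"; its earlier items are electrolytes, proteins, glucose, urea and bilirubin.
- The hematology list ("hemoglobin, hematocrit, MCV, MCH, MCHC, RDW, reticulocytes, platelets" and the white-cell items) has no coagulation test.
- The urinalysis list ("specific gravity, pH, blood, protein, glucose, bilirubin, WBC, RBC, epithelial cells, bacteria, casts, and crystals") has none either.

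Table 6-1 has rows for hematology and "Clinical Chemistry" but no visible row for PT or INR.

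Section 7.3 covers the same events in prose. For a confirmed laboratory trigger, it asks the investigator to consider interrupting treatment. For liver events as a group, it makes stopping the drug conditional on that being appropriate.

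**The concern.** In the range > 3 to ≤ 5 × ULN the two definitions overlap. For a patient without symptoms, jaundice or any other liver-event criterion, INR alone decides whether treatment must stop at once or whether a repeat test within a week is enough. The protocol calls for INR only after the patient has been classed as a liver event. A site that follows the text exactly would not obtain the value needed to choose the row.

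A mandatory safety stop is at stake. Two patients with the same liver status could be handled differently because one site ordered INR on its own initiative and the other did not. The planned outputs would not reveal this: the liver summaries in SAP Section 2.7.3 name AST, ALT, total bilirubin and ALP, not INR. The study has no data monitoring committee (Section 8.4).

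**Working it through.** No sample-size or error-rate figure is involved. The check reads the liver rules against the tests the protocol schedules, then counts the doses still to come.

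**Step 1. Is INR measured before classification?** It is not in Sections 6.5.1.1, 6.5.1.2 or 6.5.1.3, nor in a visible row of Table 6-1. Some Table 6-1 rows are blacked out in the public copy, but Sections 6.5.1.1 to 6.5.1.5 run without a gap, so a hidden coagulation panel is unlikely. Elsewhere PT/INR appears only in the follow-up column of Table 14-2, in liver-event rows.

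**Step 2. Could LFT be meant to include INR?** Probably not. Section 7.3 describes trigger follow-up as repeating the parameter that was abnormal, which here is ALT or AST. Table 14-2 spells out PT/INR in other rows and does not do so in this one. The abbreviation list expands LFT without giving components.

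**Step 3. What happens in each band when INR is not yet known?**

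| Finding | Handling under Table 14-2 | Does missing INR matter? |
|---|---|---|
| ALT/AST > 3 to ≤ 5 × ULN, asymptomatic, no jaundice, TBL ≤ 2 × ULN, no other liver-event criterion | Repeat LFT, close observation; no INR named, no stop required | Yes |
| > 5 to ≤ 8 × ULN, asymptomatic | Liver event; PT/INR in follow-up; stop if the rise lasts more than 2 weeks | The INR rule can be detected from follow-up |
| > 8 × ULN | Immediate stop | No |
| > 3 × ULN with listed symptoms | Immediate stop | No |
| Potential Hy's Law case | Immediate stop | No |
| Jaundice | Immediate stop | No |
| Isolated TBL > 2 × ULN | Repeat within 48 hours, stop if it persists; PT/INR in follow-up | Not in this way |

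The gap is confined to the first row.

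**Step 4. How many doses could follow?** The three doses are at Day 1, Week 4 and Week 8 (Section 5.5.4). Chemistry is scheduled at screening, Day 1, Week 4, Week 12 and Week 24 (Table 6-1), with none at Week 8. If the result arrives after that visit's dose:

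- Day 1 finding: 3 − 1 = 2 doses left (Weeks 4 and 8).
- Week 4 finding: 3 − 2 = 1 dose left (Week 8).
- Week 12 or Week 24 finding: 3 − 3 = 0 doses left.

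If a Week 4 result were known before dosing, the Week 4 dose would also be in question, making two. A Day 1 finding is less likely, because exclusion criterion 14 removes patients with ALT/AST at or above 3 × ULN at initial screening.

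**Step 5. Does another rule force the stop?** The list of mandatory stops in Section 5.6.2 has no specific liver criterion, only general safety-risk and investigator-judgment items. Section 7.3 is conditional where Table 14-2 is mandatory, so these two passages also conflict for the INR row itself.

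**The case against.** The strongest reply is that absence from the routine panels is not in itself a fault. Gamma-GT is also missing from the chemistry list, yet Table 14-2 asks for it alongside PT/INR, so the protocol plainly relies on event-driven liver tests. Nothing prevents an INR in the affected band: monitoring is discretionary, Section 11 provides for extra safety assessments in individual cases, and Section 5.6.2 requires a stop when the investigator judges that a laboratory abnormality rules out continuing. The laboratory manual mentioned in Section 6.5.1 was not available, and it might trigger an INR automatically.

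Much of this stands. A reader might infer that the INR stop can never operate, or that any patient who meets it would be handled as a lesser trigger. The documents support neither. PT/INR is listed in follow-up for > 5 to ≤ 8 × ULN, so the rule can be detected there. The > 8 × ULN, symptomatic, Hy's Law and jaundice rows stop treatment without it. In the one remaining band, such a patient could be misclassified, not necessarily would be.

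The reply does not close the gap. In the other bands the event-driven test follows a classification that does not need it; in this band the classification depends on it. The protocol does not mention an automatic INR, and discretion permits the test without calling for it. A mandatory stop should not depend on a site's initiative.

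**Conclusion.** The point holds for one band: asymptomatic ALT/AST > 3 to ≤ 5 × ULN with no jaundice, TBL ≤ 2 × ULN and no other liver-event criterion. Such a patient could be dosed again, typically once after a Week 4 finding and twice after a Day 1 finding, without the value that separates two rows with opposite actions.

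The conclusion assumes that LFT does not include INR and that the laboratory manual adds no automatic INR.

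The number of patients cannot be estimated from the documents and is likely very small. A reader might infer a count by assuming that 0.5% to 2% of the 880 patients exceed 3 × ULN (0.005 × 880 = 4.4; 0.02 × 880 = 17.6, or about 4 to 18). The documents give no such rate. The figure would also count patients above 5 × ULN, symptomatic patients and everyone with a normal INR, so it does not measure misclassification.

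The efficacy analysis is unaffected. The point still merits correction because a stated mandatory stop rests on data the protocol does not call for when the choice is made.

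**What to change.** Reconcile Section 6.5.1, Section 7.3 and Tables 14-1 and 14-2 so that the INR row does not depend on a value the protocol does not call for when ALT/AST first exceeds 3 × ULN. If the laboratory manual already provides for the test, the protocol should say so.

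In the same edit, reconcile the conditional stop wording for liver events in Section 7.3 with "Discontinue the study treatment immediately" in Table 14-2. The medical team decides how; no threshold or clinical action is proposed here.

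The cost is protocol wording and, depending on the choice made, at most a coagulation result in a few patients at a repeat blood draw that is already required.

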U NOVARTIS

Clinical Development

AMG 334 (erenumab)

CAMG334A2302 / NCT03333109

A 12-week double-blind, randomized, multi-center study, comparing the efficacy and safety of once monthly subcutaneous AMG 334 against placebo in adult episodic migraine patients (EMPOwER)

Statistical Analysis Plan (SAP)

Property of Novartis For business use only May not be used, divulged, published or otherwise disclosed without the consent of Novartis

| Date | Time point | Reason for update | Outcome for update | Section and title impacted (Current) |
|-----------------|---------------|-----------------------------------|-----------------------|---|
| 2-Feb 2018 | | Initial SAP, version 1.0 | | |
| 26-Feb- 2020 | | Version 2.0 | Amendment 1 | Section 2.1.3: definition for cumulative MMD |
| | | | | Section 2.12: ANCOVA model for cumulative MMD |
| | | | | Section 2.71: add analysis for treatment- related AEs/SAEs |
| | | | | Section 2.1.3.1: reference to document "Important derivations in AMG" |
| | | | | Section 2.3.1: definition of DBTP completer |
| | | | | Section 2.1.1.4: add definition for Treatment Failure of Prior Migraine Prophylactic Medications |
| | | | | Section 5.1.5.3.2: remove the number of failed Prior Migraine Prophylactic Medications as covariates as strata is present |
| | | | | Table 2-2: update start date to be consistent with baseline definition |
| | | | | Table 2-1: remove day 1 (as no more needed, part of baseline visit) |
| | | | | Section 2.1.1.1 add EOT definition |
| | | | | Table 2-2: safety FU start and end date |
| | | | | Table 2-1: FU target day |
| | | | | Section 2.1.1: added definition screening value for C-SSRS |
| | | | | Section 2.5.5, section 4: added supplementary analysis for long lasting migraine events |
| | | | | Section 5.1.2: imputation of end date for concomitant medication |

Document History – Changes compared to previous final version of SAP

| Date | Time point | Reason for update | Outcome for update | Section and title impacted (Current) |
|------|---------------|----------------------|--------------------|--|
| | | | | Section 5.1.4: imputation of start/end date for alternative migraine therapies |
| | | | | Section 2.1.1: age is collected and not birth year. |
| | | | | Definition of BDI-II moved from section 2.1.3.1 to 2.1.3.2 |
| | | | | Section 2.3.2: clarification regarding multiple race. Remove listing with child bearing status. Added stratification of summary of prior migraine prophylactic treatment by medication category. categorical variable added regarding baseline disease characteristics as "Number of prior prophylactic treatment failures" |
| | | | | Section 2.4.2: prior medications only listed |
| | | | | Section 2.7.1: summary of SAE by CTCAE removed |
| | | | | Section 2.7.3: add clarification (newly occurring) |
| | | | | Section 2.7.4: urine pregnancy results not listed (data not available) |
| | | | | Section 2.12: added analysis for monthly migraine-specific medication treatments days as per protocol objective |
| | | | | Section 2.1.3.2 and section 5.1.2: remove part related to flag in eCRF for treatment- emergent (as not in the CRF) |
| | | | | Section 5.1.5.1: imputation rule for monthly average severity of migraine pain and hours of migraine headache removed as not among the endpoints |
| | | | | Section 5.1.5.3.2: paragraph about 50% responder as MI analysis not planned for this endpoint |
| | | | | Section 1: date of study protocol final |
| | | | | Section 2.1.3.2: add clarification regarding |

concomitant medication

| Date | Time point | Reason for update | Outcome for update | Section and title impacted (Current) | |
|------|---------------|----------------------|--------------------|---|--|
| | | | | Section 2.1.3.1: modification of headache, migraine and migraine attack definition for aura-only event (cannot be linked to medication). Reason added in section 4 | |
| | | | | | |
| | | | | | |
| | | | | Section 2.7.1: add summary of AE for entire study period | |
| | | | | Section 2.5.2: 95% CI for LSmeans not displayed in shell | |
| | | | | Section 2.6.2: testing strategy updated. Clarification on dichotomous endpoint added. | |
| | | | | Section 2.6.5.1: Clarification added regarding subgroup analysis. | |

Table of contents

| | Table | of conten | nts | 5 |
|---|--------|------------|--|----|
| | List o | f abbrevi | ations | 7 |
| 1 | Introc | luction | | 9 |
| | 1.1 | Study d | lesign | 9 |
| | 1.2 | Study o | bjectives and endpoints | 10 |
| 2 | Statis | tical metl | nods | 13 |
| | 2.1 | Data an | alysis general information | 13 |
| | | 2.1.1 | General definitions | 14 |
| | | 2.1.2 | Visit and analysis windows | 17 |
| | | 2.1.3 | Definition of terms included in study endpoints | 21 |
| | 2.2 | Analysi | is sets | 28 |
